2.5.3 Missing data

For categorical variables, patients with missing data are not included in calculations of percentages unless otherwise specified. When relevant, the number of patients with missing data is presented.

Handling of computation of treatment duration if investigational medicinal product end of treatment date is missing

For the calculation of the treatment duration, the date of the last dose of IMP is equal to the date of last administration reported on the end-of-treatment case report form page. If this date is missing, the exposure duration should be left as missing.

The last dose intake should be clearly identified in the case report form and should not be approximated by the last returned package date.

Handling of medication missing/partial dates

No imputation of medication start/end dates or times will be performed. If a medication date or time is missing or partially missing and it cannot be determined whether it was taken prior or concomitantly, it will be considered a prior, concomitant, and posttreatment medication.

Handling of adverse events with missing or partial date/time of onset

Missing or partial adverse event onset dates and times will be imputed so that if the partial adverse event onset date/time information does not indicate that the adverse event started prior to treatment or after the treatment-emergent adverse event period, the adverse event will be classified as treatment-emergent. No imputation of adverse event end dates/times will be performed. These data imputations are for categorization purpose only and will not be used in listings. No imputation is planned for date/time of adverse event resolution.

Handling of adverse events when date and time of first investigational medicinal product administration is missing

When the date and time of the first IMP administration is missing, all adverse events that occurred on or after the day of randomization should be considered as treatment-emergent adverse events. The exposure duration should be kept as missing.

The last dose intake should be clearly identified in the case report form and should not be approximated by the last returned package date.

Handling of missing assessment of relationship of adverse events to investigational medicinal product

If the assessment of the relationship to IMP is missing, then the relationship to IMP has to be assumed and the adverse event considered as such in the frequency tables of possibly related adverse events, but no imputation should be done at the data level.

Handling of missing severity of adverse events

If the severity is missing for 1 of the treatment-emergent occurrences of an adverse event, the maximal severity on the remaining occurrences will be considered. If the severity is missing for all the occurrences, a “missing” category will be added in the summary table.

Handling of potentially clinically significant abnormalities

If a patient has a missing baseline he will be grouped in the category “normal/missing at baseline.”

For PCSAs with 2 conditions, one based on a change from baseline value or a normal range and the other on a threshold value, with the first condition being missing, the PCSA will be based only on the second condition.

For a PCSA defined on a threshold and/or a normal range, this PCSA will be derived using this threshold if the normal range is missing; eg, for eosinophils the PCSA is >0.5 GIGA/L or $>\text{ULN}$ if $\text{ULN} \geq 0.5$ GIGA/L. When ULN is missing, the value 0.5 should be used.

Measurements flagged as invalid by the laboratory will not be summarized or taken into account in the computation of PCSA values.

2.5.4 Windows for time points

For the safety assessment, the reference date for the derivation of relative days of events or findings will be the date of first IMP administration. Selected safety variables will be summarized by the analysis window define in [Table 6](#) for the by visit descriptive analysis. All available values from central lab will be assigned to the appropriate visit window. In the event of multiple measurements of the same test in the same window, the one closest to the targeted visit date will be used for the by-visit summary. If they are at the same distance to the target day, the latest one will be used. For procedures planned on Visit 2, if it is done on the same date as the first IMP injection but the performance time is missing, it will belong to Visit 2 time window.

Table 6 - Time window for safety endpoints

Visit	Target Day	Time windows for						
		Vital signs	Hematology, biochemistry, urinalysis	Serum Pregnancy test, Hepatitis and HIV serology tests, height	Urine Pregnancy test	Physical examination	Body weight	ECG
Visit 1 (Week - 4±1)	-28±7	<-14	<-14	1-		<-14	1-	<-14
Visit 2 (Week 0)	1	-14-1-	-14-1-		1-	-14-1-		-14-1-
Visit 3 (Week 2)	15	1-21						

Visit	Target Day	Time windows for						
		Vital signs	Hematology, biochemistry, urinalysis	Serum Pregnancy test, Hepatitis and HIV serology tests, height	Urine Pregnancy test	Physical examination	Body weight	ECG
Visit 4 (Week 4)	29	22-42	1 ⁺ -42		1 ⁺ -42			
Visit 5 (Week 8)	57	43-70	43-70		43-70			
Visit 6 (Week 12)	85	71-126	71-126		71-98		1 ⁺ -126	
Visit 7 (Week 16)	113				99-126			
Visit 8 (Week 20)	141				127-154			
Visit 9 (Week 24)	169	127-210	127-210		155-182	1 ⁺ -266		127-210
Visit 10 (Week 28)	197				183-210			
Visit 11 (Week 32)	225				211-238			
Visit 12 (Week 36)	253	211-280	211-308		239-266			211-308
Visit 13 (Week 40)	281				267-294			
Visit 14 (Week 44)	309	281-336			295-322			
Visit 15 (Week 48)	337				323-350			
Visit 16 (Week 52)	365	337-406	309-406		351-406	267-406	1 ⁺ -406	309-406
Visit 17 (Week 56)	393							
Visit 18 (Week 60)	421							
Visit 19 (Week 64)	449	>406	>406		>406	>406	>406	>406

1⁺: up to 1st dose date/time;

1⁺: after 1st dose date/time;

For the efficacy assessment, the reference date for the derivation of relative days of events or findings will be the randomization day. If a patient receives IMP prior to the randomization by mistake, the reference date of efficacy assessment will be the date of the first IMP administration for that patient. For the primary analyses, all available values of scheduled measurements will be assigned to the appropriate visit window according to [Table 7](#). In the event of multiple measurements of the same test in the same window, the one closest to the targeted visit date will

be used for the by-visit summary. If they are at the same distance to the target day, the latest one will be used.

Table 7 - Time window for efficacy variables

Visit	Target Day	Time windows for			SGRQ	EQ-5D-5L	BODE
		Pre-bronchodilator Spirometry	Post-bronchodilator Spirometry				
Visit 1 (Week -4±1)	-28±7	<-14	<-14				
Visit 2 (Week 0)	1	-14-1-	-14-1-		1-	1-	1-
Visit 3 (Week 2)	15	1+-21	1+-21				
Visit 4 (Week 4)	29	22-42	22-42		1+-56		
Visit 5 (Week 8)	57	43-70	43-70				
Visit 6 (Week 12)	85	71-126	71-126		57-126		
Visit 7 (Week 16)	113						
Visit 8 (Week 20)	141						
Visit 9 (Week 24)	169	127-210	127-210		127-210	1+-266	
Visit 10 (Week 28)	197						
Visit 11 (Week 32)	225						
Visit 12 (Week 36)	253	211-280	211-308		211-308		
Visit 13 (Week 40)	281						
Visit 14 (Week 44)	309	281-336					
Visit 15 (Week 48)	337						
Visit 16 (Week 52)	365	337-406	309-406		309-406	>266	>1+
Visit 17 (Week 56)	393						
Visit 18 (Week 60)	421						
Visit 19 (Week 64)	449	>406	>406		>406		

1-: up to randomization and before 1st dose date/time;

1+: after randomization or 1st dose date/time

For the pharmacokinetics/pharmacodynamics variables summary, the reference date for the derivation of relative days of measurements will be the date of first IMP administration if the patient is treated with study treatment, or the randomization date if the patient is not treated. Pharmacokinetics /pharmacodynamics variables will be summarized by the analysis window defined in [Table 8](#) for the by visit descriptive analyses. All available values of measurements will be assigned to the appropriate visit window. In the event of multiple measurements of the same test in the same window, the one closest to the targeted visit date will be used for the by-visit summary. If they are at the same distance to the target day, the latest one will be used. For procedures planned on Visit 2, if it is done on the same date as the first IMP injection but the performance time is missing, it will belong to Visit 2 time window.

Table 8 - Time window for pharmacokinetics/pharmacodynamics variables

Visit	Target day	Time windows for						
		FeNO post-Bronchodilator	Serum dupilumab concentration	Anti-drug antibodies	Total IgE	PARC	Eotaxin-3	Fibrinogen
Visit 1 (Week -4±1)	-28±7							
Visit 2 (Week 0)	1	1-	1-	1-	1-	1-	1-	1-
Visit 3 (Week 2)	15		1*-21					
Visit 4 (Week 4)	29	1*-42	22-42				1*-56	
Visit 5 (Week 8)	57	43-70	43-70					
Visit 6 (Week 12)	85	71-126	71-126	1*-126	1*-224		57-126	
Visit 7 (Week 16)	113							
Visit 8 (Week 20)	141							
Visit 9 (Week 24)	169	127-210	127-210	127-266		127-266		1*-266
Visit 10 (Week 28)	197							
Visit 11 (Week 32)	225							
Visit 12 (Week 36)	253	211-308	211-308					
Visit 13 (Week 40)	281							
Visit 14 (Week 44)	309							
Visit 15 (Week 48)	337							

Visit	Target day	Time windows for						
		FeNO post-Bronchodilator	Serum dupilumab concentration	Anti-drug antibodies	Total IgE	PARC	Eotaxin-3	Fibrinogen
Visit 16 (Week 52)	365	309-406	309-406	267-406	225-406	1 ⁺ -406	267-406	267-406
Visit 17 (Week 56)	393							
Visit 18 (Week 60)	421							
Visit 19 (Week 64)	449	>406	>406	>406	>406	>406	>406	>406

1-: up to 1st dose date/time or randomization if patient is not treated;

1+: after 1st dose date/time or randomization date if patient is not treated;

2.5.5 Unscheduled visits

Unscheduled visit measurements of laboratory data, vital signs, and ECG will be included in the by-visit summaries, computation of baseline, worst values, and PCSAs.

2.5.6 Pooling of centers for statistical analyses

Due to the large number of centers, the randomization is stratified by country. Due to small sample size in some countries, the countries will be pooled into regions as defined below for the analyses:

- Latin America: Argentina, Colombia, Peru, Chile, Brazil and Mexico;
- East Europe: Russia, Ukraine, Poland, Bulgaria, Lithuania, Latvia, Czech Republic, Slovakia, Hungary, Romania, Serbia;
- Western Countries: Australia, Belgium, France, Portugal, Spain, Germany, Netherlands, United Kingdom, South Africa, Canada, USA, Greece.

2.5.7 Statistical technical issues

Not applicable.

3 INTERIM ANALYSIS

An interim analysis is planned when the information fraction is ≥ 0.92 based on follow-up time for the primary endpoint of annualized rate of moderate or severe COPD exacerbations over a 52-week treatment period. The information fraction at the time of interim analysis will be estimated using a conservative approach assuming all ongoing patients complete the 52-week treatment period. All participants will have complete follow-up for the key secondary endpoint of change from baseline in FEV₁ at Week 12. The purpose of this interim analysis is to potentially demonstrate efficacy when $\geq 92\%$ of the information fraction for the primary endpoint is available, but prior to all patients completing the 52-week treatment period, as COPD is a disease with a high unmet medical need.

To control the overall type I error at $\alpha=0.05$, the Kim DeMets approach (9) will be used with the power parameter rho (ρ) determined based on the information fraction observed at the time of the interim analysis and to maintain an $\alpha=0.049$ at the final analysis (Table 9). The details of the hierarchical testing strategy at interim analysis and final analysis are specified in Section 2.4.4.3.

Table 9 - Kim-DeMets alpha spending function to control the overall alpha at 0.05

Information fraction	Rho (ρ)	α at interim analysis	α at final analysis
0.92 to <0.93	12	0.018	0.049
0.93 to <0.94	12	0.020	0.049
0.94 to <0.95	13	0.022	0.049
0.95 to <0.96	14	0.024	0.049
0.96 to <0.97	15	0.027	0.049

This interim analysis will be performed by independent statisticians that support the DMC and are separated from personnel involved in the trial conduct. The DMC will review the unblinded result of the primary endpoint and will communicate if the criterion for efficacy is met. The DMC is established and will continue the regular review of unblinded safety data as described in the DMC charter. In the event that statistical significance is demonstrated on the primary endpoint the additional inferential analyses will be performed by the unblinded Sponsor team. To maintain study integrity with respect to the subsequent visits, follow-up and final analyses after this interim analysis, a dissemination plan will be written. This plan will clearly identify two independent study teams (blinded team and unblinded team) and provide further details on the unblinding plan. People involved in the conduct of the study (patients, Investigators, Site Staff, and the blinded Study and Project Team) will have no access to unblinded patient level data, individual patient treatment codes, or unblinded tables or figures (details described in the Dissemination plan).

4 DATABASE LOCK

The database lock for primary analysis is planned based on the results of the interim analysis (see more details in [Section 3](#)).

If efficacy at the interim analysis is not demonstrated, the database lock for the primary analysis will be planned based on the date when the last patient completes the Week 52 visit or discontinues from the study before Week 52. Analyses will be based on all data collected up to this database lock and will be considered as the final analysis of the CSR. Additional data between this database lock and last patient completing last visit will be summarized in a CSR addendum.

If efficacy at the interim analysis is demonstrated, then the interim analysis database lock will be considered the primary analysis for all endpoints. The database lock for final analysis is planned when all patients complete the Week 52 visit or discontinue from the study before Week 52 but may occur when all patients complete the Week 64 visit or discontinue from the study.

5 SOFTWARE DOCUMENTATION

All summaries and statistical analyses will be generated using SAS version 9.4 or higher.

7 LIST OF APPENDICES

- Appendix A: Potentially clinically significant abnormalities (PCSA) criteria
- Appendix B: St. George's respiratory questionnaire
- Appendix C: SGRQ scoring algorithm
- Appendix D: EXACT questionnaire
- Appendix E: EQ-5D
- Appendix F: BODE
- Appendix G: High dose of inhaled corticosteroids: adults
- Appendix H: Definition of anaphylaxis
- Appendix I: List of opportunistic infections
- Appendix J: Selection criteria for AE groupings
- Appendix K: Handling of missing data
- Appendix L: Summary of primary estimand for main endpoints

Appendix A Potentially clinically significant abnormalities criteria

**CRITERIA for POTENTIALLY CLINICALLY SIGNIFICANT ABNORMALITIES
for phase 2/3 studies
(From BTD-009536 – 21-MAY-2014)**

Parameter	PCSA	Comments
Clinical Chemistry		
ALT	By distribution analysis: >3 ULN >5 ULN >10 ULN >20 ULN	Enzymes activities must be expressed in ULN, not in IU/L. Concept paper on DILI – FDA draft Guidance Oct 2007. Internal DILI WG Oct 2008. Categories are cumulative. First row is mandatory. Rows following one mentioning zero can be deleted.
AST	By distribution analysis: >3 ULN >5 ULN >10 ULN >20 ULN	Enzymes activities must be expressed in ULN, not in IU/L. Concept paper on DILI – FDA draft Guidance Oct 2007. Internal DILI WG Oct 2008. Categories are cumulative. First row is mandatory. Rows following one mentioning zero can be deleted.
Alkaline Phosphatase	>1.5 ULN	Enzymes activities must be expressed in ULN, not in IU/L. Concept paper on DILI – FDA draft Guidance Oct 2007. Internal DILI WG Oct 2008.
Total Bilirubin	>1.5 ULN >2 ULN	Must be expressed in ULN, not in μ mol/L or mg/L. Categories are cumulative. Concept paper on DILI – FDA draft Guidance Oct 2007. Internal DILI WG Oct 2008.
Conjugated Bilirubin >35% Total Bilirubin and TBILI>1.5 ULN		Conjugated bilirubin dosed on a case-by-case basis.
ALT and Total Bilirubin	ALT>3 ULN and TBILI>2 ULN	Concept paper on DILI – FDA draft Guidance Oct 2007. Internal DILI WG Oct 2008. To be counted within a same treatment phase, whatever the interval between measurement.
CPK	>3 ULN >10 ULN	FDA Feb 2005. Am J Cardiol April 2006. Categories are cumulative. First row is mandatory. Rows following one mentioning zero can be deleted.

CRITERIA for POTENTIALLY CLINICALLY SIGNIFICANT ABNORMALITIES
for phase 2/3 studies
(From BTD-009536 – 21-MAY-2014)

Parameter	PCSA	Comments
CLcr (mL/min) (Estimated creatinine clearance based on the Cokcroft-Gault equation)	<15 (end stage renal disease) ≥15 - <30 (severe decrease in GFR) ≥30 - <60 (moderate decrease in GFR) ≥60 - <90 (mild decrease in GFR) ≥90 (normal GFR)	FDA draft Guidance 2010 Pharmacokinetics in patients with impaired renal function-study design, data analysis, and impact on dosing and labeling
eGFR (mL/min/1.73m ²) (Estimate of GFR based on an MDRD equation)	<15 (end stage renal disease) ≥15 - <30 (severe decrease in GFR) ≥30 - <60 (moderate decrease in GFR) ≥60 - <90 (mild decrease in GFR) ≥90 (normal GFR)	FDA draft Guidance 2010 Pharmacokinetics in patients with impaired renal function-study design, data analysis, and impact on dosing and labeling
Creatinine	≥150 µmol/L (Adults) ≥30% change from baseline ≥100% change from baseline	Benichou C., 1994.
Uric Acid		Harrison- Principles of internal Medicine 17 th Ed., 2008.
Hyperuricemia	>408 µmol/L	
Hypouricemia	<120 µmol/L	
Blood Urea Nitrogen	≥17 mmol/L	
Chloride	<80 mmol/L ≥115 mmol/L	
Sodium	≤129 mmol/L ≥160 mmol/L	
Potassium	<3 mmol/L ≥5.5 mmol/L	FDA Feb 2005.
Total Cholesterol	≥7.74 mmol/L	Threshold for therapeutic intervention.
Triglycerides	≥4.6 mmol/L	Threshold for therapeutic intervention.
Lipasemia	≥3 ULN	
Amylasemia	≥3 ULN	
Glucose		
Hypoglycaemia	≤3.9 mmol/L and <LLN	ADA May 2005.
Hyperglycaemia	≥11.1 mmol/L (unfasted); ≥7 mmol/L (fasted)	ADA Jan 2008.
HbA1c	>8%	
Albumin	≤25 g/L	
CRP	>2 ULN or >10 mg/L (if ULN not provided)	FDA Sept 2005.
Hematology		
WBC	<3.0 Giga/L (Non-Black); <2.0 Giga/L (Black) ≥16.0 Giga/L	Increase in WBC: not relevant. To be interpreted only if no differential count available.
Lymphocytes	>4.0 Giga/L	

[figure not shown]
**CRITERIA for POTENTIALLY CLINICALLY SIGNIFICANT ABNORMALITIES
for phase 2/3 studies
(From BTD-009536 – 21-MAY-2014)**

[figure not shown]
Parameter	PCSA	Comments
Neutrophils	<1.5 Giga/L (Non-Black);<1.0 Giga/L (Black)	International Consensus meeting on drug-induced blood cytopenias, 1991. FDA criteria.
Monocytes	>0.7 Giga/L	
Basophils	>0.1 Giga/L	
Eosinophils	>0.5 Giga/L or >ULN (if ULN≥0.5 Giga/L)	Harrison- Principles of internal Medicine 17 th Ed., 2008.
Hemoglobin	≤115 g/L (Male); ≤95 g/L (Female) ≥185 g/L (Male); ≥165 g/L (Female) Decrease from Baseline ≥20 g/L	Criteria based upon decrease from baseline are more relevant than based on absolute value. Other categories for decrease from baseline can be used (≥30 g/L, ≥40 g/L, ≥50 g/L).
Hematocrit	≤0.37 v/v (Male); ≤0.32 v/v (Female) ≥0.55 v/v (Male); ≥0.5 v/v (Female)	
RBC	≥6 Tera/L	Unless specifically required for particular drug development, the analysis is redundant with that of Hb. Otherwise, consider FDA criteria.
Platelets	<100 Giga/L ≥700 Giga/L	International Consensus meeting on drug-induced blood cytopenias, 1991.
Urinalysis		
pH	≤4.6 ≥8	
Vital signs		
HR	≤50 bpm and decrease from baseline ≥20 bpm ≥120 bpm and increase from baseline ≥20 bpm	To be applied for all positions (including missing) except STANDING.
SBP	≤95 mmHg and decrease from baseline ≥20mmHg ≥160 mmHg and increase from baseline ≥20 mmHg	To be applied for all positions (including missing) except STANDING.
DBP	≤45 mmHg and decrease from baseline ≥10 mmHg ≥110 mmHg and increase from baseline ≥10 mmHg	To be applied for all positions (including missing) except STANDING.
Orthostatic Hypotension		
Orthostatic SDB	≤-20 mmHg	
Orthostatic DBP	≤-10 mmHg	
Weight	≥5% increase from baseline ≥5% decrease from baseline	FDA Feb 2007.
ECG		
		Ref.: ICH E14 guidance (2005) and E14 Q&A (2012), and Cardiac Safety Research Consortium White Paper on PR and QRS (Nada et al. Am Heart J. 2013; 165(4): 489-500)

CRITERIA for POTENTIALLY CLINICALLY SIGNIFICANT ABNORMALITIES
for phase 2/3 studies
(From BTD-009536 – 21-MAY-2014)

[figure not shown]
Parameter	PCSA	Comments
HR	
<50 bpm
 
<50 bpm and decrease from baseline \geq20 bpm
 
<40 bpm
 
<40 bpm and decrease from baseline \geq20 bpm
 
<30 bpm
 
<30 bpm and decrease from baseline \geq20 bpm
 
>90 bpm
 
>90 bpm and increase from baseline \geq20bpm
 
>100 bpm
 
>100 bpm and increase from baseline \geq20bpm
 
>120 bpm
 
>120 bpm and increase from baseline \geq20 bpm
	Categories are cumulative
PR	
>200 ms
 
>200 ms and increase from baseline \geq25%
 
>220 ms
 
>220 ms and increase from baseline \geq25%
 
>240 ms
 
>240 ms and increase from baseline \geq25%
	Categories are cumulative
QRS	
>110 ms
 
>110 msec and increase from baseline \geq25%
 
>120 ms
 
>120 ms and increase from baseline \geq25%
	Categories are cumulative
QT	>500 ms	
QTc	
Absolute values (ms)
 
>450 ms
 
>480 ms
 
>500 ms
 
Increase from baseline
 
Increase from baseline]30-60] ms
 
Increase from baseline >60 ms
	
To be applied to any kind of QT correction formula.
 
Absolute values categories are cumulative
 
QTc >480 ms and ΔQTc>60 ms are the 2 PCSA categories to be identified in individual subjects/patients listings.

[figure not shown]

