2.4.5 Analyses of safety data

The summary of safety results will be presented by treatment group. All safety data collected up to the primary analysis cut-off date (either the IA cut-off date or cut-off date when last patient completes Week 52) will be included.

General common rules

All safety analyses will be performed on the safety population as defined in [Section 2.3.2](#), unless otherwise specified, using the following common rules:

- The baseline value is defined as the last available value before the first dose of IMP.
- The potentially clinically significant abnormality (PCSA) values are defined as abnormal values considered medically important by the Sponsor according to predefined criteria/thresholds based on literature review and defined by the Sponsor for clinical laboratory tests and vital signs and ECG [Appendix A]
- PCSA criteria will determine which patients had at least 1 PCSA during the treatment-emergent adverse event period, taking into account all evaluations performed during the treatment-emergent adverse event period, including nonscheduled or repeated evaluations. The number of all such patients will be the numerator for the on-treatment PCSA percentage

- The treatment-emergent PCSA denominator by group for a given parameter will be based on the number of patients assessed for that given parameter in the treatment-emergent adverse event period by treatment group on the safety population.
- For quantitative safety parameters based on central laboratory/reading measurements, descriptive statistics will be used to summarize results and change from baseline values by visit and treatment group. Summaries will include the endpoint value and/or the worst on-treatment value. The endpoint value is commonly defined as the value collected at the end of treatment. If this value is missing, this endpoint value will be the closest value prior to the end of treatment epoch. The worst value is defined as the nadir and /or the peak post-baseline (up to the end of treatment epoch or EOT) according to the direction (minimum or maximum) of the abnormality as defined in the PCSA list
- The analysis of the safety variables will be essentially descriptive and no systematic testing is planned. Relative risks versus placebo and their 95% confidence intervals may be provided, if relevant
- All safety values including unscheduled measurements will be assigned to the appropriate safety analysis visit window defined in [Section 2.5.3](#).

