2.4.5.3 Analyses of laboratory variables

The summary statistics (including number, mean, median, Q1, Q3, standard deviation, minimum and maximum) of all laboratory variables (central laboratory values and changes from baseline) will be calculated for each visit or study assessment (baseline, each postbaseline time point, last on-treatment and/or worst on-treatment value) by treatment group. For each continuous parameters listed in [Section 2.1.4.3](#), mean changes from baseline with the corresponding standard error will be plotted over time in each treatment group. This section will be organized by biological function as specified in [Section 2.1.4.3](#).

The incidence of PCSAs (list provided in Appendix A) at any time during the treatment-emergent adverse event period will be summarized by biological function and treatment group whatever the baseline level and/or according to the following baseline status categories:

- Normal/missing
- Abnormal according to PCSA criterion or criteria

For parameters for which no PCSA criteria are defined, similar table(s) using the normal range will be provided.

For PCSA analyses, the laboratory measurements obtained at either scheduled or unscheduled visits should be used; and, both the centralized and local test results should be used, as long as their available dates/time is different from each other's. Centralized data will be used preferentially to the local measures in the PCSA analyses when measurements are performed on the same date and at the same time for a given laboratory test.

Additional analyses for potential drug-induced liver injury

The following additional analyses will be performed for potential drug-induced liver injury:

- Time to onset of the initial ALT elevation ($>3 \times \text{ULN}$), AST elevation ($>3 \times \text{ULN}$) and total bilirubin elevation ($>2 \times \text{ULN}$) will be analyzed with K-M curves, presented by intervention group.
- A graph of distribution of peak values of ALT versus peak values of total bilirubin will also be presented.

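### The creatinine-clearance PCSA list in SAP Appendix A includes the normal band and covers every value, so the any-band rate is 100% and the 60 to <90 row is not a reliable renal signal

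*SAP*

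**What the plan says.** SAP 2.4.5 (Analyses of safety data) sets three rules.

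- Definition: PCSA "values are defined as abnormal values considered medically important by the Sponsor".
- Numerator: "PCSA criteria will determine which patients had at least 1 PCSA during the treatment-emergent adverse event period".
- Denominator: the "number of patients assessed for that given parameter in the treatment-emergent adverse event period by treatment group".

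SAP 2.4.5.3 applies these to the laboratory data: "The incidence of PCSAs (list provided in Appendix A) at any time during the treatment-emergent adverse event period" is tabulated irrespective of baseline, and/or split into patients whose baseline is normal or missing and patients whose baseline is abnormal by the PCSA criteria.

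The criteria are in SAP Appendix A. The CLcr entry in the PCSA column reads "<15 (end stage renal disease) ≥15 - <30 (severe decrease in GFR) ≥30 - <60 (moderate decrease in GFR" and continues "≥60 - <90 (mild decrease in GFR) ≥90 (normal GFR". The MDRD eGFR entry repeats the same five bands. Neither carries a change-from-baseline condition or a cumulative note. ALT, AST and CPK have the comment "Categories are cumulative. First row is mandatory", and total bilirubin and several ECG rows are also marked cumulative.

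SAP 2.5.1 derives CLcr by Cockcroft-Gault and gives no MDRD formula. Protocol 9.4.2 (Table 10, laboratory parameters) promises shift tables against baseline status. SAP 2.4.5.3 does not mention them.

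**The concern.** A PCSA table compares the arms on how many patients had a value worth worrying about. That fails when the list of worrying values includes the normal range. Three things go wrong if the CLcr rule is programmed as written.

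- Any observed CLcr satisfies some listed criterion, so the overall CLcr PCSA rate carries no information.
- The middle bands are bounded on both sides and are counted at any time with no reference to baseline. A patient enters the row labelled as a mild decrease by falling from above 90, by rising from below 60, or by never leaving it.
- The baseline split needs a working definition of a normal baseline, and the list does not supply one.

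At stake is a renal safety table whose row labels do not describe the patients counted in them. In the 60 to <90 row, harm could show as a lower percentage in the treated arm.

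**Working it through.** The plan states no figure for this point, so there is nothing to reproduce. The first three steps need no assumptions. The fourth does, because the documents give no CLcr distribution.

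**1. Coverage.** The bands are <15, 15 to <30, 30 to <60, 60 to <90 and ≥90. Assigning every value from 0 to 300 mL/min in steps of 0.001 gives a minimum of 1 and a maximum of 1 band per value. Any-band incidence among assessed patients is therefore 100% in each arm by construction.

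**2. Direction.** A patient at 45 who rises to 65 enters the 60 to <90 row. A patient who goes from 95 through 75 to 50 is counted in two rows labelled as decreases. Now take a uniform 20% fall and ignore measurement noise. A patient ends in 60 to <90 if the starting value was between 60/0.8 = 75 and 90/0.8 = 112.5. The row loses patients who started at 60 to <75 and gains those who started at 90 to <112.5. It goes down under harm whenever the first group is larger than the second.

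**3. Baseline split.** If any listed band counts as abnormal, every observed baseline is abnormal and the normal-or-missing group holds only missing baselines. If the split is read row by row, a baseline of 45 counts as normal for the 60 to <90 row.

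**4. Size.** Assumptions: 200,000 patients per setting; baseline CLcr normal with mean 70, 80 or 95 and SD 25 mL/min, truncated to 15-200; within-patient CV 8% or 12%; and one baseline plus seven post-baseline values, matching the chemistry visits in SAP 2.1.4.3 (Weeks 4, 8, 12, 24, 36, 52 and 64). The true change is either none or a uniform 20% fall. At CV 8%, the percentage of patients ever counted in each row is as follows (no change → 20% fall):

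| Row (mL/min) | Mean 70 | Mean 80 | Mean 95 |
|---|---|---|---|
| <15 | 1.7 → 2.5 | 0.6 → 0.9 | 0.1 → 0.1 |
| 15 to <30 | 7.2 → 11.4 | 3.2 → 5.8 | 0.7 → 1.6 |
| 30 to <60 | 40.9 → 63.0 | 28.4 → 52.6 | 12.9 → 31.9 |
| 60 to <90 | 62.3 → 52.6 | 63.9 → 65.2 | 53.2 → 74.5 |
| ≥90 | 33.2 → 11.2 | 48.7 → 20.4 | 71.0 → 40.5 |
| Worst band worse than baseline band | 23.8 → 63.7 | 24.2 → 67.8 | 21.6 → 69.5 |

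Across both CVs, the five band percentages sum to 138-171%, because one patient can appear in several rows. With no true change, 18-47% of patients newly entering the 60 to <90 row came from below 60.

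With a log-normal distribution (same means and SD, CV 8%), the 60 to <90 row moves from 60% to 44% at mean 70 and from 61% to 76% at mean 95. Over both distribution shapes and both CVs, the worse-than-baseline measure rises from 22-36% to 59-75%.

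**The case against.** The strongest reply has four parts.

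**The definition already excludes normal values.** A sensible programmer would treat ≥90 as a reference category, and no passage explicitly plans a pooled any-CLcr-PCSA row. With ≥90 as normal and everything lower as abnormal, the baseline split also works. That reading is reasonable, but the SAP does not state it, and Appendix A contradicts it by putting the band in the PCSA column. It also leaves the 60 to <90 row mixing directions.

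**The rows still detect harm.** A reader might infer that the CLcr table cannot show renal harm at all. The documents do not support that. The 30 to <60 row rises clearly under a fall (28.4% to 52.6% at mean 80), the 15 to <30 row also rises, and no one can enter <15 by improving. Nor does every improvement count as a decrease: a rise to ≥90 is counted as normal.

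**Some of the complaint applies to any threshold.** Being counted in several rows also happens with cumulative categories, and a baseline already past the cut-point affects absolute limits such as creatinine ≥150 µmol/L. This stands. So does the point that, under no true change, entries from below are measurement noise, not real improvement.

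**Renal safety is covered elsewhere.** Creatinine and blood urea nitrogen have their own rows, worst on-treatment values may be summarised, and the protocol promises shift tables. This limits the damage. However, the SAP does not carry the shift tables forward, and it gives renal function nothing like the return-to-baseline summary it adds for liver tests.

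On eGFR, a reader might infer a second broken table. Appendix A is a generic phase 2/3 list that includes analytes outside this study's panel, and no MDRD derivation is given, so an eGFR table may never be produced.

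**Conclusion.** The point holds in a limited form and is minor. Without any assumption, the CLcr list includes a value labelled normal against the SAP's own definition, its bands cover every value, the any-band rate is 100%, and a rise into 60 to <90 counts as a mild decrease. If any listed band counts as abnormal, the normal-or-missing baseline group holds only missing baselines.

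The 60 to <90 row is unreliable because its direction under harm depends on where patients start. In the settings tabulated above, a uniform 20% fall lowers it by 9.7 points (62.3 - 52.6), leaves it nearly flat (+1.3), or raises it by 21.3 (74.5 - 53.2). Those sizes rest on assumed CLcr distributions, within-patient CVs of 8-12% and a uniform fall. The possibility of a reversal follows from the band limits alone.

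The damage is confined to the CLcr PCSA table, and to an eGFR table if one is run. The rows below 60 mL/min and the creatinine and blood urea nitrogen rows remain usable, and the safety analysis is descriptive with no systematic testing planned.

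**What to change.** Amend Appendix A and SAP 2.4.5.3 for CLcr, and for eGFR if it is to be reported:

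1. State that ≥90 is the normal reference category and not a PCSA.
2. Classify each patient once, by the lowest CLcr in the treatment-emergent adverse event period. Name that window, because the worst value in SAP 2.4.5 stops at the end of the treatment epoch.
3. Present a baseline-band by worst-band shift table, which also meets the commitment in Protocol 9.4.2. Count a PCSA when the worst band is worse than the baseline band.
4. Handle missing baselines under the existing convention in SAP 2.5.3, which groups them with normal.

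The cost is a few lines of text and a small programming change, with no new data. The revised measure is not free of noise: it still flags 22-36% of patients under no change in the simulated settings, so it should be read as a comparison between arms. The CLcr rows will differ from the sponsor's generic PCSA list. The generic bands can be shown alongside for cross-study comparison.
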